1.2. STUDY DIAGRAM

Abbreviations: 2L=second line; *EGFR*mt=epidermal growth factor receptor mutation; ICR=independent central review; NSCLC=non-small cell lung cancer; ORR= overall response rate; pts=patients; TKI=tyrosine kinase inhibitor

1.3. SCHEDULE OF EVENTS

Table 1: Schedule of Events for Phase 1 (Parts A and B)

Procedure	Screening Period Within 28 Days prior to first dose	Treatment Period							Follow-up Period		Notes
		PK Lead-in ^a	Cycle 1 (21 days)			Cycle 2 (21 days)		Cycles ≥ 3 (21 days)	Safety Follow-up ^b	Survival Follow-up	
		Day -3	Day 1	Day 8 (± 1 day)	Day 15 (± 3 days)	Day 1 (± 3 days)	Day 8 (± 3 days)	Day 1 (± 3 days)	30 (+3) days after last dose		
EGFR C797S status (pre-screening informed consent)	See Notes										Only if central pre-screening done. Can be done any time prior to screening.
Written informed consent (main study)	X										To be obtained prior to any study related procedures.
Review inclusion / exclusion criteria	X										All patients in Part A2 and B must have documented C797S EGFRmt. See Section 4.1 and Section 4.2
Demographics/ Medical history	X										Including prior antitumor treatment
Physical examination	X	X	X	X		X		X	X		Within 24 hours prior to dosing. May be symptom directed during treatment period. Examination of skin should be performed at each timepoint. See Section 7.1
Ophthalmological examination	X	As clinically indicated							X		See Section 7.1.5
Height and weight	X	X	X			X		X	X		Height at screening only
Vital signs	X	X	X	X	X	X	X	X	X		Heart rate, blood pressure, and body temperature. See Section 7.1
Hematology	X	X	X	X	X	X	X	X	X		Assessment prior to first day of dosing may be done up to 72 hours prior to dosing

											(Section 7.1.4) All other assessments may be done within 24 hours prior to dosing See Section 7.1
Chemistry	X	X	X	X	X	X	X	X	X		Assessment prior to first day of dosing may be done up to 72 hours prior to dosing (Section 7.1.4) All other assessments may be done within 24 hours prior to dosing See Section 7.1
Coagulation	X	X	X			X		X	X		Assessment prior to first day of dosing may be done up to 72 hours prior to dosing (Section 7.1.4) All other assessments may be done within 24 hours prior to dosing See Section 7.1
Urinalysis	X	X	X			X		X	X		Assessment prior to first day of dosing may be done up to 72 hours prior to dosing (Section 7.1.4) All other assessments may be done within 24 hours prior to dosing. See Section 7.1
Pregnancy test	X	X	(X)			X		X			For WOCBP only: Serum pregnancy test required at screening only. See Section 7.1 (X) not required for patients in Part A1
Adverse events	X	X	X						X	(X)	From signing ICF through 30-day safety follow-up or until start of new anticancer therapy, whichever is earlier. See Section 10.1 (X) only related SAE Investigator becomes aware of
Concomitant medications	X	X	X						X		From signing ICF through 30-day safety follow-up or until start of new anticancer therapy, whichever is earlier. See Section 6.4
ECOG Performance Status	X		X			X		X	X		

PK sampling		See Table 13 / Table 14									Table 13 for QD dosing / Table 14 for BID
Central ECG		See Table 13 / Table 14									To be performed as triplicates. For patients in Part A1 only. See Section 7.1.2
Local ECG ^c	X		X			X		X	X		12-lead ECG. Not needed if central ECG done the same day. Additional ECG monitoring as clinically indicated. See Section 7.1.2
Echocardiography/ MUGA	X							X			From Cycle 4 onwards, every 4 cycles or as clinically indicated. See Section 7.1.3
cfDNA blood samples			X			X		X	X		From Cycle 3 onwards, every other cycle. After 12 months, every 3 cycles.
Tumor tissue samples	X					(X)			(X)		Baseline sample optional for patients in Part A1. See Section 11.2 (X) On-treatment biopsy optional; can be done at one of these timepoints
Radiologic tumor assessment	X		X						(X)	(X)	Every 6 weeks (±7 days) from C1D1 irrespective of cycle. After 12 months, every 9 weeks (±7 days). (X) Patients who discontinue study treatment without radiographic PD will continue every 9 weeks (±7 days) until radiographic PD. See Section 7.1
Survival status										X	Every 3 months (±2 weeks); collect also further anticancer therapies. See Section 7.1 . For patients in Part A2 and B only
Administration of TAS3351		X	X								Continuous dosing See Section 6.1

^a PK lead-in period applies to Part A1 only: During PK lead-in period, patients will receive a single dose of TAS3351 3 days prior to the start of multiple TAS3351 dosing in Cycle 1 with subsequent PK blood collection. The PK blood sample collection times during the PK lead-in period may be found in [Table 13](#). For these patients, 72-hour post-dose assessments occur on C1D1, prior to C1D1 dosing.

^b The 30-day Safety Follow-up visit should be performed 30 days (± 3 days) following the last dose of study therapy. If the patient starts new anticancer therapy within 30 days of the last dose of study medication, the 30-day Safety Follow-up visit should be performed before the start of new anticancer therapy. Only if the patient is unable to return to the study site, a follow-up phone call can be made by the study site to collect any new safety information that occurred during the Safety Follow-up period.

^c ECG assessment for C1D1, and D1 of C2 and beyond should be conducted pre-dose (up to 30 minutes prior to dosing). ECG should be performed on D1 of every cycle. All ECGs should be performed in triplicate on Day 1 of Cycles 1 to 3 for all patients. After C3D1, ECGs are not required to be performed in triplicate unless clinically indicated.

Abbreviations: AE=adverse event; C=cycle; cfDNA=cell-free DNA; D=day; DLT=dose-limiting toxicity; ECG=electrocardiogram; ECOG=Eastern Cooperative Oncology Group; EOT=end of therapy; ICF=informed consent form; MUGA=multi-gated acquisition scan; PD=progressive disease; PK=pharmacokinetics; QD=once daily; RECIST=Response Evaluation Criteria in Solid Tumors; SAE=serious adverse event; WOCBP=women of childbearing potential

Note: (X) = See notes for details.

Table 2: Schedule of Events for Phase 2 (Part C)

Procedure	Screening Period Within 28 Days prior to first dose	Treatment Period			Follow-up Period		Notes
		Cycle 1 (21 days)		Cycle ≥2 (21 days)	Safety Follow-up ^a	Survival Follow-up	
		Day 1	Day 8 (±1 day)	Day 1 (±3 days)	30 (+3) days after last dose		
EGFR C797S status (pre-screening informed consent)	See Notes						Only if central pre-screening done. Can take place any time prior to screening
Written informed consent (Main study)	X						To be obtained prior to any study related procedures. Can take place any time before Day 1
Review inclusion / exclusion criteria	X						All patients must have documented C797S EGFR mt
Demographics/Medical history	X						Including prior antitumor treatment
Physical examination	X	X		X	X		Within 24 hours prior to dosing. May be symptom directed during treatment period. Examination of skin should be performed at each timepoint.
Ophthalmological examination	X	As clinically indicated			X		See Section 7.1.5
Height and weight	X	X		X	X		Height at screening only
Vital signs	X	X	X	X	X		Heart rate, blood pressure, body temperature
Hematology	X	X	X	X	X		Assessment prior to first day of dosing may be done up to 72 hours prior to dosing (Section 7.1.4) All other assessments may be done within 48 hours prior to dosing, See Section 7.1
Chemistry	X	X	X	X	X		Assessment prior to first day of dosing may be done up to 72 hours prior to dosing (Section 7.1.4) All other assessments may be done within 48 hours prior to dosing. See Section 7.1

Procedure	Screening Period Within 28 Days prior to first dose	Treatment Period			Follow-up Period		Notes
		Cycle 1 (21 days)		Cycle ≥2 (21 days)	Safety Follow-up ^a	Survival Follow-up	
		Day 1	Day 8 (±1 day)	Day 1 (±3 days)	30 (+3) days after last dose		
Coagulation	X	X		X	X		Assessment prior to first day of dosing may be done up to 72 hours prior to dosing (Section 7.1.4) All other assessments may be done within 48 hours prior to dosing. See Section 7.1
Urinalysis	X	X		X	X		Assessment prior to first day of dosing may be done up to 72 hours prior to dosing (Section 7.1.4) All other assessments may be done within 48 hours prior to dosing. See Section 7.1
Pregnancy test	X	X		X			For WOCBP only: Serum pregnancy test required at screening only. See Section 7.1
Local ECG ^b	X	X		X	X		12-lead ECG. Additional ECG monitoring as clinically indicated. See Section 7.1
Adverse events	X	X			X	(X)	From signing ICF through 30-day safety follow-up. (X) only related SAE Investigator becomes aware of
Concomitant medications	X	X	X	X	X		From signing ICF through 30-day safety follow-up.
ECOG Performance Status	X	X		X	X		
Patient reported outcomes	X			X	X		During treatment period, to be assessed as close as possible to the tumor assessments.
PK sampling		See Table 13					
cfDNA blood samples		X		X	X		From C3D1 onwards, every other cycle. After 12 months, every 3 cycles
Tumor tissue samples	X			(X)	(X)		(X) On-treatment biopsy optional; can be done at one of these timepoints

Procedure	Screening Period Within 28 Days prior to first dose	Treatment Period			Follow-up Period		Notes
		Cycle 1 (21 days)		Cycle ≥2 (21 days)	Safety Follow-up ^a	Survival Follow-up	
		Day 1	Day 8 (±1 day)	Day 1 (±3 days)	30 (+3) days after last dose		
Radiologic tumor assessment	X	X			(X)	(X)	Every 6 weeks (±7 days) from C1D1 irrespective of cycle. After 12 months, every 9 weeks (±7 days). (X) Patients who discontinue study treatment without radiographic PD will continue every 9 weeks (±7 days) until radiographic PD. See Section 7.1
Survival status						X	After discontinuation of treatment, survival follow-up should occur every 3 months (±2 weeks), collection of further anticancer therapies. See Section 7.1
Administration of TAS3351		X					Continuous dosing. See Section 6.1

^a The 30-day Safety Follow-up visit should be performed 30 days (+3 days) following the last dose of study therapy. If the patient starts new anticancer therapy within 30 days of the last dose of study medication, the 30-day Safety Follow-up visit should be performed before the start of new anticancer therapy. Only if the patient is unable to return to the study site, a follow-up phone call can be made by the study site to collect any new safety information that occurred during the Safety Follow-up period.

^b ECG assessment for C1D1, and D1 of C2 and beyond should be conducted pre-dose (up to 30 minutes prior to dosing). ECG should be performed on D1 of every cycle. All ECGs should be performed in triplicate on Day 1 of Cycles 1 to 3 for all patients. After C3D1, ECGs are not required to be performed in triplicate unless clinically indicated.

Abbreviations: AE=adverse event; C=cycle; cfDNA=cell-free DNA; D=day; DLT=dose-limiting toxicity; ECG=electrocardiogram; ECOG=Eastern Cooperative Oncology Group; EOT=end of therapy; ICF=informed consent form; PD=progressive disease; PK=pharmacokinetics; QD=once daily; RECIST=Response Evaluation Criteria in Solid Tumors; SAE=serious adverse event; WOCBP=women of childbearing potential

Table 3: Schedule of Events – Study Extension Phase

	Treatment Period	Safety Follow-up 30 (±7) Days After Last Dose	Notes
	At Least Every 3 Cycles ^a		
Physical examination	X	X	May be symptom directed during treatment period. Examination of skin should be performed at each timepoint.
Vital signs	X	X	Heart rate, blood pressure, and body temperature
Local ECG	X	X	12-lead ECG
Weight	X	X	
Hematology	X	X	See Section 7
Chemistry	X	X	See Section 7
Pregnancy test	X		Serum or urine pregnancy test
Concomitant medications, AE assessments	X	X	Collect from the time main informed consent is signed through 30 days after administration of the last dose of study therapy or until the start of new anticancer therapy, whichever is earlier. See Section 6.4.1 and Section 10.1
Tumor assessments / scans	X		Tumor assessments may be performed as necessary to determine continued benefit from treatment, every 3 cycles (±14 days), or as clinically indicated, until clinical or radiographic PD. See Section 7.1.1

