Patients will receive TAS3351 study medication until documentation of progressive disease (PD), unacceptable toxicity, or any other discontinuation or withdrawal criterion is met.

Criteria for Evaluation:

Efficacy:

Efficacy will be evaluated based on tumor assessments (including CT)/magnetic resonance imaging [MRI] performed by Investigator/local radiologist according to RECIST v1.1 guideline.

Safety:

Safety and tolerability will be assessed based on the incidence of treatment-emergent adverse events (TEAEs, including serious adverse events [SAEs] and DLTs), dose modifications, clinical laboratory parameters, 12-lead electrocardiograms (ECGs), measurement of ejection fraction, ophthalmologic abnormalities, and vital signs. Grading of TEAEs will be performed based on CTCAE, Version 5.0. PK matched central ECG will be performed as triplicates for patients enrolled in Part A1.

Pharmacokinetics

The plasma concentrations of TAS3351 as well as its active metabolite, TAS-05-14317, will be measured by a validated LC/MS/MS method. The PK data obtained in the Dose Escalation phase will be analyzed by non-compartmental analysis to derive key PK parameters including but not limited to C_{max} , T_{max} , AUC, and $T_{1/2}$. The concentration data by time and study day obtained in the Expansion phase and/or Phase 2 will be summarized descriptively.

Biomarkers

For patient eligibility, the *EGFR*mt status has to be determined by a CLIA certified (US), locally certified (outside of the US), or the study central laboratory based on tumor tissue or plasma cfDNA. For patients enrolled based on local results, *EGFR*mt status will be confirmed at the Sponsor's designated study central laboratory post-enrollment.

For exploratory biomarker analysis, changes in circulating free tumor DNA (cfDNA) from blood samples collected at baseline and on-treatment may be assessed retrospectively for any change of genomic variants following TAS3351 treatment and any association with clinical outcomes. Changes in biomarkers from optional tumor samples (eg, pEGFR) collected

on-treatment may be analyzed relative to baseline expression, if paired tumor samples are available.

Patient Reported Outcome

Patients' health-related quality of life, symptoms, functioning, and general well-being will be captured using the EORTC QLQ-C30 and EQ-5D-5L questionnaires.

Statistical Methods:

Sample Size Calculation:

- Part A: Phase 1 Dose Escalation

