6. STUDY TREATMENT

6.1. Study Drug Administration

TAS3351 will be administered orally once daily (QD) on Days 1 to 21 of a 21-day cycle. Patients enrolled in Part A1 will also be administered a single dose of TAS3351 on Cycle 1 Day -3 during the PK Lead-in Period. If PK, pharmacodynamic, and/or safety data indicate, twice daily (BID) dosing of TAS3351 may also be explored.

- TAS3351 should be taken at approximately the same time every day on an empty stomach and should be taken with water. Patients should not consume food 2 hours before and ending 1 hour after taking TAS3351 but will be allowed to drink water during this period. Patients should be instructed to swallow the tablets whole and not to chew or crush them.
- In the event of a dosing delay up to 12 hours (6 hours for BID dosing) after the scheduled dosing time, the patient should still take that day's dose. If the dosing delay is >12 hours (6 hours for BID dosing) or if the patient vomits after a dose, the patient should skip that dose and continue with the planned subsequent dose (skipped or missed doses should not be made up).

On PK sampling days, TAS3351 should be administered on-site after the pre-dose PK sample collection (Table 13). Actual dosing time will be recorded.

Patients will receive TAS3351 until disease progression, unacceptable toxicity, or any other discontinuation criterion or withdrawal criterion is met (Section 5.4, Section 5.6).

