4.2. Populations for Analysis

The analysis populations in the study are defined in [Table 3](#).

Table 3: Definitions of Analysis Populations

Analysis Population	Definition
All Consenting Population	All patients who signed an informed consent form (ICF).
All Treated Population	All patients who received at least one dose of the study drug. This is the primary population for dosing, efficacy and safety analyses.
DLT Evaluable Population	All patients in the Dose Escalation, except backfill patients, who either experienced a DLT during the 1st cycle of treatment including PK lead-in period, or who completed the 1st cycle without experiencing a DLT and with at least 80% of planned study treatments administered. This is the specific population for DLT summarization.
PK Analysis Population	All patients who received at least one dose of study drug and have at least one post-dose TAS3351 and/or TAS-05-14317 plasma concentration measurement will be evaluated for PK; unless significant protocol

	deviations may have affected the data or if key dosing information is missing. This is the primary population for PK analysis.
PK/ECG Analysis Population	All patients who received at least one dose of study drug, have a baseline and at least one post-dose ECG value, and have time-matched plasma concentrations to at least one post-dose ECG value.
Pharmacodynamic/Biomarker Analysis Population	All patients in the All-Treated Population who have at least one evaluable baseline and one evaluable post-dose pharmacodynamic/biomarker datapoint for analyses.

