7. DEFINITIONS AND CONVENTIONS FOR DATA HANDLING

7.1. Baseline Period

Baseline evaluations or events will be defined as evaluations or events that occur before the date and time of the first dose of study drug. Evaluations on the same date and time of the first dose of study drug will be considered as baseline evaluations.

In cases where the time (onset time of event or evaluation time and dosing time) is missing or not collected, the following definitions will apply:

- Pre-treatment AEs will be defined as AEs with an onset date prior to but not including the day of the first dose of study drug
- Baseline evaluations will be defined as evaluations with a date on or prior to the day of first dose of study drug

If there are multiple valid assessments, the assessment that is closest to the day (and time if collected) of the first dose of study drug will be used as the baseline in the analyses. If multiple assessments are collected on the same date (and time, if collected), the assessment with the latest database entry date (and time, if collected) will be considered as baseline.

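### Under once-daily dosing, Part A1 has no scheduled cfDNA draw before the first TAS3351 dose, so the planned baseline versus on-treatment comparison cannot be made from scheduled samples

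*Protocol*

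**What the plan says.** - **Dosing.** Footnote a to protocol Table 1 says of the PK lead-in in Part A1: "patients will receive a single dose of TAS3351 3 days prior to the start of multiple TAS3351 dosing in Cycle 1". Section 6.1 agrees: "Patients enrolled in Part A1 will also be administered a single dose of TAS3351 on Cycle 1 Day -3". The footnote also fixes the interval: "For these patients, 72-hour post-dose assessments occur on C1D1, prior to C1D1 dosing".
- **cfDNA schedule.** The Table 1 row has entries at C1D1, Cycle 2 Day 1, Day 1 of Cycles 3 and later, and Safety Follow-up. Screening and Day -3 are blank. The note gives only the later frequency, "From Cycle 3 onwards, every other cycle. After 12 months, every 3 cycles", with no exception for Part A1 and no instruction to draw before dosing.
- **Intended use.** The synopsis plans to assess "changes in circulating free tumor DNA (cfDNA) from blood samples collected at baseline and on-treatment". Section 11.3 likewise describes samples from before and during treatment.
- **Baseline.** SAP Section 7.1 defines baseline as "evaluations or events that occur before the date and time of the first dose of study drug". SAP Table 2 starts the A1 treatment period at the PK lead-in.
- **Biomarker population.** SAP Table 3 asks for "at least one evaluable baseline and one evaluable post-dose pharmacodynamic/biomarker datapoint". It does not name cfDNA.
- **A row that was adapted.** The pregnancy-test row has a Day -3 entry, and its note on C1D1 ends "X) not required for patients in Part A1".

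**The concern.** In Parts A2 and B, C1D1 is the first dosing day, so a sample taken before that day's dose is a true baseline. In Part A1 with a lead-in, the same column of the table is a post-exposure visit. The cfDNA row treats the two as equivalent.

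Part A1 is where all six planned dose levels are tested, and protocol Section 12.7.5 plans biomarker summaries by dose level and schedule. Section 4.2.1 lists pharmacodynamics among the inputs to the recommended Phase 2 dose. Tissue is optional in A1, so cfDNA is its only non-optional serial biomarker sample. If C1D1 is taken as baseline by default, change has a different meaning in A1 than in A2 and B. A pre-dose sample that was never drawn cannot be recovered at the analysis stage.

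**Working it through.** No sample-size or power figure bears on this point. The check sets the schedule against the SAP definitions.

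**1. Is the blank real?** The cfDNA row splits into the full 12 columns of Table 1, with entries at C1D1, Cycle 2 Day 1, Cycles 3 and later, and Safety Follow-up. The hematology row, read the same way, shows entries at both Screening and Day -3. The drug-administration row shows Day -3 and C1D1. The blank is therefore not a shifted column.

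**2. Interval from first dose to first cfDNA draw.** There is no Day 0, so Day -3 to Day 1 is 3 days: 3 × 24 = 72 hours, which matches footnote a. Section 6.2.1 lets the start of Cycle 1 be delayed after a lead-in, so the interval can be longer.

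**3. Does C1D1 qualify as baseline?** First dose in A1 is Day -3 (protocol Section 6.1, SAP Table 2), and baseline must precede it (SAP 7.1). The SAP 7.1 rule for missing times accepts a sample dated on the first-dose day, but for A1 that day is Day -3, so the rule does not rescue C1D1. Scheduled pre-first-dose cfDNA draws in A1 under once-daily dosing: 0.

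**4. Is there a baseline elsewhere?** Section 11.1 ties biomarker collection to the Schedule of Events. Mandatory blood for central testing (Section 11.2) covers Parts A2, B and C only. Some A1 patients may have plasma cfDNA from pre-screening or eligibility testing, or optional screening tissue, but none of these is a required baseline draw.

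**5. Comparison with other serial measures.** Vital signs, hematology, chemistry, coagulation and urinalysis have Screening and Day -3 entries. Table 13 places an ECG before the Day -3 dose. ECOG status, echocardiography/MUGA, tissue and imaging have Screening entries. Among serial measures that need a baseline, only cfDNA has nothing scheduled before the A1 first dose.

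**6. Patients concerned.** Up to 40 in A1: 40/60 = 67% of Part A, 40/(40 + 20 + 40) = 40% of Phase 1, and 40/200 = 20% of the study. Loss from the biomarker population ranges from 0 (every patient has another qualifying baseline marker) to 40 (none has).

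**7. Effect of using C1D1 as baseline (illustration only).** Let B be the true baseline, f the fractional fall by C1D1, and L a later level. The documents do not give f; take 20% to 50% as an assumption.
- Absolute change: true fall B − L, apparent fall B(1 − f) − L, so the fall is understated by fB, or 20% to 50% of B.
- Percent change: the understatement is (L/B) × f/(1 − f).
  - For L/B = 0.1: 0.1 × 0.25 = 2.5 percentage points (f = 20%) to 0.1 × 1 = 10 points (f = 50%).
  - For L/B = 0.5: 0.5 × 0.25 = 12.5 points to 0.5 × 1 = 50 points.
  - For complete clearance (L = 0): zero.

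The distortion is thus small for deep falls and large for shallow ones, if an early fall occurs at all.

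**The case against.** The best case against acting is that cfDNA is exploratory and its assessment is optional and retrospective. No primary or secondary endpoint and no escalation rule uses it. The C797S target population sits in A2, B and C, where C1D1 can serve as baseline. Biomarker methods are in a separate plan that is not among these documents, and that plan may handle A1 differently. All of this stands and limits the weight of the point. It does not remove it: a separate plan can redefine baseline, but it cannot supply a sample that was not collected.

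Several stronger readings are tempting, and the documents do not support them:
- **A1 patients drop out of the biomarker population.** SAP Table 3 accepts any evaluable baseline marker, so optional tissue or an earlier cfDNA result may keep a patient in.
- **A1 patients have no pre-treatment cfDNA at all.** Inclusion criterion 5 and Section 11.2 allow eligibility or pre-screening on plasma cfDNA. What is missing is a scheduled study draw.
- **C1D1 is the only early genotype.** Documented EGFR mutation status is an entry condition in A1 too.
- **Early falls are hidden most at the highest doses.** This is plausible, but nothing in the documents shows it.

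The count of 40 is also a ceiling. If twice-daily dosing is explored, Table 14 and Section 8.3.1 begin A1 sampling at C1D1 with no lead-in, and a pre-dose C1D1 draw would then be a baseline. Section 6.1 states the Day -3 dose for A1 without that exception, so these passages need reconciling.

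**Conclusion.** The concern holds in a limited form. Under once-daily dosing, the schedule gives Part A1 no cfDNA draw before first exposure, while the synopsis and Section 11.3 plan a comparison that needs one. Up to 40 patients are affected. The conclusion rests on the lead-in dose being given as written and on SAP 7.1 governing the cfDNA baseline.

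The number lost from the biomarker population and the size of any bias cannot be determined from the documents. The percentages in step 7 of the working depend on an assumed early fall. The consequence is confined to an exploratory analysis. Correction is still worthwhile, because the loss is permanent for each patient enrolled and the remedy is nearly free.

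**What to change.** **Table 1, at the next amendment.** Where a lead-in dose is given, move the A1 cfDNA draw from C1D1 to Day -3, pre-dose, and mark C1D1 as not needed for A1, as the pregnancy-test row already does. For A1 patients without a lead-in (for example under twice-daily dosing, if none is used), keep C1D1 and state that it is drawn before dosing.

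**A1 patients already enrolled.** Label the C1D1 sample as post-first-dose and do not pool it with A2/B baselines. Use a central pre-screening cfDNA sample as baseline only if it was taken after the last prior therapy and within a stated window before first dose. The window is needed because Table 1 sets no limit on how early pre-screening may take place. Record these rules in the biomarker analysis plan.

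**Cost.** One table cell, a note, and a few lines in the biomarker plan. The number of blood draws is unchanged, and A1 patients already have blood taken on Day -3.
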